### **5.2 Pelvic Floor Exercises (PFE) in PD**

There is limited research of PFE in PD. These are simple interventions that can be easily applied in a clinical setting (such as an educational video/handout). One uncontrolled pilot study in 20 patients with PD showed a significant improvement in episodes of urinary incontinence from baseline to follow-up after an 8-week, 5-visit course of PFE-based behavioral therapy (Vaughn 2011).

This design will demonstrate the effects of PFE on OAB in PD through the placebo arm of the study. Because PFE are possibly effective with virtually no risk, they are the preferred first-line intervention, but their efficacy has not been rigorously demonstrated. In addition,

including PFE in the protocol eliminates a possible confounder, as some, but likely not all, patients may have received training in PFE and be practicing them on their own.

### **5.3 Mirabegron for OAB**

Adding mirabegron may yield greater results than PFE alone. Mirabegron is an FDA-approved treatment for OAB that has not been studied in Parkinson disease (PD). Importantly, mirabegron has a novel mechanism of action, activating Beta-3 adrenergic receptors in detrusor muscles (Chapple 2012). It is therefore expected to avoid anticholinergic side effects such as confusion, hallucinations, and constipation, to which PD patients are especially susceptible.

In phase 3 clinical trials, mirabegron demonstrated efficacy in treating OAB symptoms in a general adult population. In a sample of 1978 patients, mirabegron 50 mg daily and 100 mg daily produced statistically significant improvements over placebo in the number of incontinence episodes per 24 hours and number of micturitions per 24 hours (Khullar 2013). Incidence of adverse events (AEs) in the groups receiving mirabegron was not significantly different from AEs in a group receiving tolterodine ER 4 mg daily (Khullar 2013). This substantiated an earlier study (Chapple 2012) that found equivalent treatment effects and AE profile when comparing mirabegron 50 mg and 100 mg to tolterodine ER 4 mg in a sample of 2444 patients. This study was not placebo-controlled. Mirabegron efficacy was similarly demonstrated in a sample of 1329 patients (Nitti 2013), wherein mirabegron 50 mg and 100 mg showed statistically significant improvement over placebo in incontinence episodes and micturitions per 24 hours.

The standard starting dose of mirabegron is 25 mg daily (Prescribing Information, Astellas Pharma, Inc.). A higher dose of 50 mg daily is also approved for use, and titration to this dose will be allowed at the mid-point of the trial (after 5 weeks), as it is likely that some patients will respond better to the higher dosage.

## **6. STUDY OBJECTIVES**

### **6.1 Primary Objective**

- To compare the effects of mirabegron to the effects of placebo on the change from baseline to Visit 4 in mean daily OAB-SCS, the summation of all OAB-SCS urgency scores recorded at all voids throughout a 72-hour diary recording averaged over 3 days.

### **6.2 Secondary Objectives**

Objectives based on micturition diary:

- To compare the effects of mirabegron to the effects of placebo on the change from baseline to Visit 3 in mean daily OAB-SCS

- To compare the effects of mirabegron to the effects of placebo on the change from baseline to visit 3 and to visit 4 in mean number of micturitions per 24 hours
- To compare the effects of mirabegron to the effects of placebo on the change from baseline to visit 3 and to visit 4 in mean number of incontinence episodes per 24 hours
- To compare the effects of mirabegron to the effects of placebo on the change from baseline to visit 3 and to visit 4 in mean volume voided per micturition.

Objectives based on clinic visits:

- To compare the effects of mirabegron to the effects of placebo on the change from baseline to visit 3 and to visit 4 in Overactive Bladder questionnaire symptom severity scale (OAB-q) score
- To compare the effects of mirabegron to the effects of placebo on the change from baseline to visit 3 and to visit 4 in Non-Motor Symptoms Scale (NMSS) score, which includes questions about cognition, psychosis, and constipation, in addition to urinary symptoms.
- To compare the effects of mirabegron to the effects of placebo on the change from baseline to visit 3 and to visit 4 in Patient Perception of Bladder Condition (PPBC).
- To compare the effects of mirabegron to the effects of placebo on the change from visit 3 and to visit 4 in Subject's Global Impression of Change (SGI-C).

## 7. INVESTIGATIONAL PLAN

### 7.1 Overall Study Design

This study is a randomized, double-blind, placebo-controlled 10-week study of mirabegron as add-on therapy to an educational intervention of behavioral modification including pelvic floor exercise (PFE) in a cohort of 40 PD subjects over the age of 30 with overactive bladder (OAB). Active drug will be mirabegron 25mg daily with optional up-titration to 50mg daily at visit 3. . Subjects will be enrolled based on response to an overactive bladder questionnaire at baseline –visit 2. Voiding diaries (72-hr) will be utilized following screening visit, Phone visit 1, and phone visit 2. In the diaries, subjects will record the time of each micturition and/or urgency episode, urine volume with each void, any episode of incontinence, and the severity of urgency as measured by the Overactive Bladder Symptom Composite Score (OAB-SCS): 1 = no urgency (normal voiding); 2 = mild (could postpone voiding for as long as necessary without fear of incontinence); 3 = moderate (could postpone voiding for a short while without fear of leakage); 4= severe (could not postpone, had to rush to the toilet); 5= urgency incontinence (could not make it to the toilet without some leakage).

Diaries will also record pelvic floor exercises. The primary outcome measure will be mean daily OAB-SCS (summation of all urgency scores recorded at all voids throughout the 72hr diary recording averaged over 3 days), visit 4 vs. visit 2-baseline. This measure accounts for both the frequency and the urgency components of OAB.

The study is composed of 4 clinic visits and 2 phone visits over the course of 11-12 weeks.

## **7.2 Enrollment**

Subjects who may qualify for this study will be identified in the context of clinical care at the EvergreenHealth Neuroscience Institute. Such eligible patients may receive a copy of the informed consent form (ICF) at the time of their clinic visit. Recruitment may also occur through local promotional opportunities, referrals from other area neurologists, urologists, EvergreenHealth Pelvic Health Rehab, and the Washington State Parkinson Disease Registry. Patients may contact the EvergreenHealth Neuroscience Institute without clinic visitation after reading a notice about the study on the Institute's website or other online postings. Subjects who are not established patients at EvergreenHealth will be offered the chance to undergo a telephone screening using an institutional review board (IRB) approved telephone screening text. Subjects will be requested to send pertinent outside medical records for chart review by the principal investigator and be scheduled for a screening visit.

## **7.3 Screening (Visit 1)**

Visit 1 is the screening visit. At this clinic visit, patients will provide written, informed consent and be assessed for eligibility (excluding those eligibility criteria requiring completion of the voiding diary). A history of the patient's PD symptoms and LUTS will be taken, and the patient's past medical history will be reviewed. Diagnosis of PD will be confirmed based on UK PD Society Brain Bank criteria (Hughes 1992). Current medication list will be reviewed, and a levodopa-equivalent daily dose will be calculated based on the patient's current PD medication list and on published conversion factors (Tomlinson 2010). Eligible subjects will have a stable PD medication regimen for 4 weeks prior to the screening visit and remain on a stable regimen for the duration of the study. Eligible patients will also not be concomitantly taking any of the prohibited medications, including none of the prohibited bladder medications for at least 14 days prior to the screening visit. The patient's history of medication allergies will be reviewed.

Physical examination will be performed, both a general medical examination including vital signs and a neurological examination. Neurological exam will include MDS-UPDRS part 3 evaluation and modified Hoehn and Yahr (HY) staging of PD (Goetz 2004). Post-void residual (PVR) will be assessed. Laboratory testing will include CBC, CMP, and urinalysis (U/A) by dipstick with reflex to urine culture if positive. Pre-menopausal women will have urine hCG measured.

The voiding diary will be dispensed to the patient and training will be provided on how to complete the diary, including instruction on how to measure void volume. The PowerPoint presentation of pelvic floor exercises will also be shown to the patient and each patient will be provided a copy to take home.

## **7.4 Baseline-(Visit 2) -Treatment Initiation**

### **7.4.1 Confirmation of Eligibility**

Patients who are deemed eligible in the screening visit will go home to complete a 72-hour voiding diary and return for Visit 2 within 7-14 days after Visit 1. At visit 2, final eligibility will be confirmed by a review of the voiding diary. Subjects eligible to continue will have urinary urgency as evidenced by at least 8 episodes of urgency scores of 2 or greater in 72 hours AND will have urinary frequency as evidenced by having EITHER 8 or more episodes of micturition per 24 hours averaged over 72 hours OR 2 or more episodes of urinary incontinence in 72 hours. In addition to confirming eligibility, the diary scoring will provide the baseline values of mean daily OAB-SCS, number of micturitions per 24 hours, number of incontinence episodes per 24 hours, and mean volume per micturition.

In addition to the diary review, medications will be reviewed again to ensure stability of the PD medication regimen and absence of any prohibited medications. Vital signs will again be measured. At any visit, if a patient is found to have systolic blood pressure over 165, diastolic blood pressure over 100 or heart rate over 100, he or she will be withdrawn from the study.

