#### **7.5 Treatment titration**

##### **7.5.1 Visit 3**

Visit 3 will occur 32-40 days after Visit 2. This visit will include the same assessments as Visit 2, including review and entry of data in the voiding diary (mean daily OAB-SCS, number of micturitions per 24 hours, number of incontinence episodes per 24 hours, and mean volume per micturition). Visit 3 will also include review of current medication list, measurement of vital signs, PVR, OAB-q, NMSS, PPBC, and SGI-C. Screening for AEs will also take place during this visit. This will include assessment of symptoms of urinary tract infection and if, in the opinion of the study physician, urinalysis is indicated, dipstick will be performed with reflex to urine culture if positive. In pre-menopausal women, screening for pregnancy risk will be performed and if, in the opinion of the study physician, pregnancy testing is indicated, urine hCG will be measured.

In addition, at Visit 3, all patients who have tolerated mirabegron 25 mg daily or matching placebo (no adverse events on this dose) will be up-titrated to mirabegron 50 mg daily (for those in the active drug arm) or matching placebo (for those in the placebo arm). This will be dispensed as two 25-mg tablets or, for those in the placebo arm, two placebo tablets. Only

those without any AE on 25 mg daily or matching placebo will be eligible to increase the dose.

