### **7.5.2 Phone Visit 2**

Phone Visit 2 will occur 70-74 days after Visit 2 and no less than 72 hours prior to Visit 4. Patients will be prompted to resume the voiding diary for 72 hours. Screening for AEs will also take place during this phone visit.

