### **10.1.2 Vital Signs**

Vital signs (blood pressure, heart rate, and respiratory rate) will be measured at each clinic visit. Subjects with BP > 165 systolic or > 100 diastolic or those with HR > 100 will be excluded at screening or discontinue study medication if this occurs while on study medication. However, they may complete other elements of the study.

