### **10.1.4 Pregnancy Status**

All pre-menopausal women will have pregnancy screening with urine hCG at baseline (Visit 1). At Visits 3 and 4, pre-menopausal women will have screening for pregnancy risk and if, in the opinion of the study physician, pregnancy testing is indicated, urine hCG will be measured. A positive urine hCG will result in discontinuation of the study drug and withdrawal of the subject from the study.

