#### 10.1.5 Post-void Residual

PVR will be measured by a bladder scan after urination at Visits 1, 3, and 4. Subjects with PVR > 200 mL will be excluded at screening or will discontinue study medication if this occurs while on study medication. Symptoms of urinary retention will be monitored throughout the study and may lead to early discontinuation of study medication; however, such subjects may complete other elements of the study.

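### Sections 7.4.1 and 10.1.2 give conflicting rules for a subject over the blood pressure or heart rate limits; following 7.4.1 at Visit 3 loses the Visit 4 primary value

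*Protocol*

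**What the plan says.** Section 7.4.1 (Protocol), within the account of Visit 2, sets a rule that reaches beyond that visit: "At any visit, if a patient is found to have systolic blood pressure over 165", or "diastolic blood pressure over 100 or heart rate over 100, he or she will be withdrawn from the study".

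Section 10.1.2 uses the same three limits. Subjects over them are excluded at screening, or "discontinue study medication if this occurs while on study medication. However, they may complete other elements of the study". The same section fixes when a breach can be found: "Vital signs (blood pressure, heart rate, and respiratory rate) will be measured at each clinic visit".

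Two neighbouring sections show how the protocol uses these terms:

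- Section 10.1.4, on pregnancy: "A positive urine hCG will result in discontinuation of the study drug and withdrawal of the subject from the study".
- Section 10.1.5, on a post-void residual above 200 mL or symptoms of retention, provides for stopping study medication; "however, such subjects may complete other elements of the study".

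Section 11.2 defines the study population as all randomised patients, analysed by intention to treat. Section 10.2.1 makes the primary outcome the change in mean daily OAB-SCS from baseline to Visit 4.

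**The concern.** For a subject on study drug, the two sections prescribe different outcomes for the same reading. Under 7.4.1 participation ends. Under 10.1.2 only the drug ends.

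The difference matters because the primary outcome comes from a diary kept late in the study. A subject removed at Visit 3 belongs to the intent-to-treat population but never reaches that diary. The loss is triggered by a measurement taken after treatment starts. The protocol itself treats that measurement as a possible drug effect, since section 10.1.2 has an on-drug stopping rule and section 11.4 plans a between-arm comparison of vital signs. Missing values could therefore differ by arm.

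A statistical analysis plan can choose how to handle a missing diary, but it cannot recover one that was never collected. Replacement of withdrawn patients, allowed in section 8.3, restores the head count but not the randomised subject's outcome.

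**Working it through.** **Can the two rules be reconciled?**

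| Possible reading | Check against the text |
|---|---|
| 7.4.1 is only an eligibility rule | It sits under an eligibility heading, but its wording covers any visit. |
| Withdrawal from the study just means stopping the drug | Section 10.1.4 lists stopping the drug and withdrawing the subject as two actions. |
| Another section decides | Section 8.3 names safety issues in general and does not choose. It also bars withdrawn patients from re-entry, so following 7.4.1 cannot be undone. |
| 10.1.2 is the stray rule | Section 10.1.5 handles post-void residual the 10.1.2 way, so 7.4.1 is the outlier. |

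**Where does the conflict matter?**

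- Visits 1 and 2, before randomisation: no one is on drug, so the rules do not collide.
- Visit 3: "Visit 3 will occur 32-40 days after Visit 2". The conflict applies.
- Unscheduled visits (section 7.7) before the last diary: the conflict applies if vital signs are taken.
- Visit 4: the diary is already complete, so a breach first found here need not cost the primary value.

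Of the 2 scheduled vital-sign checks after randomisation, 1 falls before the last diary.

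**Timing.** The last diary is prompted by telephone: "Phone Visit 2 will occur 70-74 days after Visit 2 and no less than 72 hours prior to Visit 4". Visit 4 is on day 74-82 (section 7.6).

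- Visit 3 to Phone Visit 2: shortest 70 − 40 = 30 days; longest 74 − 32 = 42 days.
- Visit 3 to Visit 4: shortest 74 − 40 = 34 days; longest 82 − 32 = 50 days.

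**What is lost under 7.4.1 after a Visit 3 breach.** The Visit 4 outcomes come from the Synopsis and section 7.6:

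- primary: OAB-SCS = 1;
- secondary: 3 from the diary (micturitions, incontinence episodes, volume per void) + 4 from the clinic (OAB-q, NMSS, PPBC, SGI-C) = 7;
- safety: Visit 4 vital signs and post-void residual.

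The Visit 3 data, including the breach reading, are kept under either rule. With 20 planned per arm, each such subject is 1/20 = 5% of an arm before any replacement.

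**Scale, on assumed rates.** The protocol gives no breach rate, effect size, SD or power, so there is no stated figure to reproduce. Suppose a proportion p of the 40 subjects breach the limits by Visit 3. The expected number lost is 40p, and the chance of at least one is 1 − (1 − p)^40.

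| Assumed p | Expected lost of 40 | Chance of at least one |
|---|---|---|
| 2% | 0.8 | 0.55 |
| 5% | 2 | 0.87 |
| 10% | 4 | 0.985 |
| 15% | 6 | 0.998 |

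For a simple two-group comparison of observed values at two-sided 0.05 (normal approximation), the difference detectable with 80% power, in SD units, is (1.960 + 0.842) × √(1/n₁ + 1/n₂). Power for an assumed effect of 0.8 SD is Φ(0.8 / √(1/n₁ + 1/n₂) − 1.960).

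| Subjects with a Visit 4 value | Detectable difference (SD) | Power at 0.8 SD |
|---|---|---|
| 20 and 20 | 0.886 | 71.6% |
| 19 and 19 | 0.909 | 69.4% |
| 18 and 18 | 0.934 | 67.0% |
| 20 and 16 | 0.940 | 66.5% |

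The loss of power is small. The main issue is avoidable missing primary data that may be related to treatment.

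**The case against.** The best case for leaving this alone has four parts.

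1. **Permission, not obligation.** Section 10.1.2 only allows continued participation. Stopping the drug and also withdrawing the subject breaks no mandatory wording there, and section 8.3 lets the investigator withdraw anyone for safety. Part of this stands: 10.1.2 as written does not secure the Visit 4 diary either. But a rule that forbids what another section permits is still a contradiction.
2. **Safety follow-up continues anyway.** Section 10.1.6 counts significantly abnormal objective findings as adverse events, and section 8.3 follows an event that leads to withdrawal, when possible, until resolution. This stands for the safety side: a breach recorded as an adverse event would be followed under either rule, and an off-drug reading would mainly show recovery. It does not supply the Visit 4 diary or post-void residual.
3. **Narrow exposure, no known rate.** Screening already excludes people over the same limits, only one scheduled check is affected, and section 7.7 does not name vital signs among the contents of an unscheduled visit. This stands and limits the importance of the point.
4. **One site, exploratory pilot.** There are no multiple sites to drift apart. That makes inconsistent handling less likely. It does not tell the single site's staff which section to follow.

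It can also be said that choosing between the safety rules is the sponsor's decision. That is fair, but the protocol's post-void residual rule and its intent-to-treat analysis both point towards 10.1.2.

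**Conclusion.** The concern holds: the protocol is wrong as written on this point and should be corrected. For a subject on drug, 7.4.1 requires withdrawal from the study where 10.1.2 allows the subject to stay. Following 7.4.1 at Visit 3 removes a randomised subject 30 to 42 days before the prompt for the primary diary and 34 to 50 days before Visit 4. It costs the primary value and all seven Visit 4 secondary outcomes for 5% of a planned arm per subject.

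The contradiction, the day ranges and the outcome count come directly from the protocol. The breach rates and the 0.8 SD effect are assumptions used only for scale. Neither the number of subjects affected nor any bias in the treatment comparison can be derived from the document.

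**What to change.** - **Section 7.4.1:** limit the withdrawal sentence to breaches found before randomisation.
- **Section 10.1.2:** for breaches after randomisation, stop study drug and ask the subject to complete all remaining scheduled diaries and visits, including the Visit 4 diary, unless consent is withdrawn. Put this in place of the present permissive wording.
- **Section 10.1.5 (optional):** use matching wording for post-void residual, so that the two parallel rules stay aligned.

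The cost is a one-sentence amendment to 7.4.1 and matching wording in 10.1.2. The diaries and visits are already scheduled, and the drug stops under either rule. The downside is that a few off-drug observations may slightly dilute the estimated drug effect. The planned intent-to-treat comparison calls for those observations.

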#### **7.4.2 Baseline Assessments**

Following confirmation of eligibility, an eligible patient will complete the baseline assessments of the OAB-q, NMSS, and PPBC during Visit 2.

#### **7.4.3 Phone visit 1**

Phone visit 1 will take place 28-32 days after Visit 2 and no less than 72 hours prior to Visit 3. Patients will be prompted to resume the voiding diary for 72 hours. Screening for AEs will also take place during this phone visit.

#### **7.5 Treatment titration**

##### **7.5.1 Visit 3**

Visit 3 will occur 32-40 days after Visit 2. This visit will include the same assessments as Visit 2, including review and entry of data in the voiding diary (mean daily OAB-SCS, number of micturitions per 24 hours, number of incontinence episodes per 24 hours, and mean volume per micturition). Visit 3 will also include review of current medication list, measurement of vital signs, PVR, OAB-q, NMSS, PPBC, and SGI-C. Screening for AEs will also take place during this visit. This will include assessment of symptoms of urinary tract infection and if, in the opinion of the study physician, urinalysis is indicated, dipstick will be performed with reflex to urine culture if positive. In pre-menopausal women, screening for pregnancy risk will be performed and if, in the opinion of the study physician, pregnancy testing is indicated, urine hCG will be measured.

In addition, at Visit 3, all patients who have tolerated mirabegron 25 mg daily or matching placebo (no adverse events on this dose) will be up-titrated to mirabegron 50 mg daily (for those in the active drug arm) or matching placebo (for those in the placebo arm). This will be dispensed as two 25-mg tablets or, for those in the placebo arm, two placebo tablets. Only

those without any AE on 25 mg daily or matching placebo will be eligible to increase the dose.

### **7.5.2 Phone Visit 2**

Phone Visit 2 will occur 70-74 days after Visit 2 and no less than 72 hours prior to Visit 4. Patients will be prompted to resume the voiding diary for 72 hours. Screening for AEs will also take place during this phone visit.

